1.1 Objectives & Hypotheses

The purpose of this study is to compare the remifentanyl requirements in deep versus moderate neuromuscular blocks during the surgical pleth index (SPI)-guided anesthesia in patients undergoing laparoscopic herniorrhaphy.

We hypothesize that deep neuromuscular block using sugammadex will reduce the total remifentanyl dose during SPI - guided anesthesia for laparoscopic herniorrhaphy, because the deep neuromuscular block is associated with less intra-operative nociception.

1.2 Background & Rationale, Significance of Selected Topic & Preliminary Data

General anesthesia results from a combination of hypnosis, antinociception, and immobility. Referring a goal-directed approach to each component, the measurement of neuromuscular paralysis or depth of anesthesia has been established as using neuromuscular monitoring or BIS (or PSI). Traditionally, clinicians utilize symptoms of the physiological stress response to nociceptive stimuli (i.e. increase of heart rate, blood pressure or lacrimation) to guide analgesic administration. However, administration of intraoperative analgesics guided by clinical symptoms alone appears to be of very limited value.

The SPI first introduced in 2007, uses pulse plethysmography and photoplethysmography, both obtained from pulse oximetry monitoring, to provide an index of the nociception–anti-nociception balance. It correlates with surgical stimuli and dosage of analgesic and predicts the effect of pain stimuli and analgesic therapy with greater certainty than common clinical parameters.

$$\text{SPI} = 100 - (\text{normalised heart beat interval} \times 0.33 + \text{normalised plethysmographic pulse wave amplitude} \times 0.67)$$

SPI had moderate correlation to the stress hormones during general anesthesia. And adjusting the remifentanyl dosage according to the SPI reduced the consumption of both remifentanyl and propofol and resulted in faster recovery compared with that according to clinical parameters. During equi-MAC anesthesia of 1.0 MAC, sevoflurane and desflurane did not show similar intraoperative remifentanyl consumption under SPI-guided opioid administration.

Excessive intraoperative administration of remifentanyl leads to opioid induced and acute opioid tolerance and opioid-induced hyperalgesia, including non-analgesic side-effects such as immunosuppression.

During laparoscopic surgery, deep neuromuscular block with sugammadex as reversal agent has been reported to reduce the postoperative pain than moderate neuromuscular block with neostigmine as reversal agent, although being controversial. The cause is postulated that at deep relaxation the tension

on the abdominal wall exerted by the intra-abdominal pressure is less harmful in comparison to the tension created during moderate relaxation.

1.3 Study Design

- This study is single center, prospective, double blinded, and randomized controlled study.
- Total **134 patients** undergoing laparoscopic herniorrhaphy included in the study.
- Inclusion criteria: American Society of Anesthesiologists (ASA) class 1, 2, and 3, laparoscopic hernia repair needing general anesthesia, and age between 19 and 85 years

Exclusion criteria: patients refusal, hyperbilirubinemia, chronic pain, opioid abuse, infection, and peripheral disease

- Using a computer-generated randomization (<http://www.random.org>), the patients were assigned into one of the 2 groups; Moderate neuromuscular block (NMB) group and Deep NMB group. Group assignment was concealed with sealed and opaque envelope. Immediately before anesthesia induction, the envelope was opened by independent investigator, who performed all interventions (control of NM block using rocuronium and reversal of NM block using study drug) but was not involved in outcome assessment. The anesthetic provider, patients, and preoperative and postoperative outcome assessors were blinded to the type of intervention (group assignment) throughout the study period.

- Patients monitoring include the noninvasive blood pressure, electrocardiogram, oximetry, and bispectral index. Anesthesia is induced with propofol of 2 mg/kg, rocuronium of 0.6 mg/kg and remifentanyl infusion using TCI (target-controlled infusion). Anesthesia was maintained with continuous infusion of remifentanyl and sevoflurane 1 MAC. After tracheal intubation, remifentanyl infusion is stopped. One minute before skin incision, the remifentanyl infusion was started in the flash mode, the target effect-site concentration of remifentanyl was initially set at 3.0 ng/ml.

Subsequently, remifentanyl infusion was continuously adjusted throughout the study period to achieve an SPI range between 20 and 50 with maintaining sevoflurane 1 MAC by an independent researcher who was blinded to the group allocation. Neuromuscular function is measured at the wrist. The TOF-SCAN generate the stimulus the ulnar nerve and measure contraction of the adductor pollicis muscle. At 15 min intervals, the TOF is measured and in the case of TOF=0, this is followed by the PTC. A bolus dose of intravenous rocuronium (5-10 mg) was used to maintain moderate (TOF count of 1-2) or deep (posttetanic count [PTC] of 1 or 2) neuromuscular blockade.

- **Moderate NMB group:** moderate NMB (T1-2), reversal using neostigmine 50 ug/kg + glycopyrrolate 10 ug/kg

- **Deep NMB group:** deep NMB (1-2 PTC), reversal using sugammadex 4 mg/kg based on actual body weight

- Primary Outcome

Remifentanil infusion rate from pneumoperitoneum to removal of laparoscope (primary outcome)

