Statistical analysis

Official title: Effects of deep neuromuscular block on surgical pleth index-guided remifentanyl administration in laparoscopic herniorrhaphy: A prospective randomized trial

NCT number: NCT04022733

Document date: Jan 18, 2022

Institution Name: Ajou University School of Medicine

The primary outcome was the infusion rate of remifentanil during pneumoperitoneum. Based on the findings of a previous study, we considered a difference in remifentanil infusion rate $>0.032 \mu\text{g}/\text{kg}/\text{min}$ (16% of mean infusion rate of remifentanil in moderate NMB under SPI-guided anesthesia for laparoscopic surgery [mean infusion rate of 0.192 (SD 0.064) $\mu\text{g}/\text{kg}/\text{min}$]) as clinically relevant. Based on a significance level of 5% and statistical power of 80%, each group required 63 subjects for analysis. We enrolled a total of 134 patients to compensate for dropouts and observational variation.

Statistical analyses were conducted using SPSS software version 25.0 (IBM, NY, USA). Data are presented as mean \pm SD, median (interquartile range), and number of patients. The normality of distribution was tested using the Kolmogorov–Smirnov/ the Shapiro–Wilk test. Continuous data were compared using a two-tailed t test when normally distributed; however, Mann-Whitney *U*-test was used for non-normally distributed data. Categorical data were compared using the Chi-square test or Fisher's exact test, as appropriate. Intergroup comparisons for repetitively measured data were performed by unpaired t-test with Bonferroni correction. *P*-values < 0.05 were considered statistically significant.

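### Does giving the post-tetanic count mainly in the deep-block arm bias the SPI-titrated remifentanil comparison enough to require a change to the plan?

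*Protocol*

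**What the plan says.** Protocol section 1.3 gives one monitoring rule for both arms: "At 15 min intervals, the TOF is measured and in the case of TOF=0, this is followed by the PTC". Rocuronium boluses are then used to "maintain moderate (TOF count of 1-2) or deep (posttetanic count [PTC] of 1 or 2) neuromuscular blockade".

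The same section says that "remifentanyl infusion was continuously adjusted throughout the study period" "to achieve an SPI range between 20 and 50 with maintaining sevoflurane 1 MAC", by a researcher blinded to allocation. It states no exception around neuromuscular checks. The primary outcome, at the end of the protocol, is the remifentanil rate between the start of pneumoperitoneum and removal of the laparoscope.

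The hypothesis in section 1.1 is that deep block lowers the remifentanil dose "because the deep neuromuscular block is associated with less intra-operative nociception".

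The SAP compares continuous outcomes with a t test or Mann-Whitney test, and repeated measurements with Bonferroni-corrected t tests. On size it says: "Based on a significance level of 5% and statistical power of 80%, each group required 63 subjects for analysis". It plans no analysis that treats time after a check separately.

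**The concern.** The rule reads as identical in the two arms, but its trigger depends on the randomised depth. A PTC requires a tetanic train, which is an electrical stimulus. Section 1.2 of the protocol describes SPI as tracking surgical stimuli and predicting the effect of painful ones. If the train raised SPI enough to prompt more remifentanil, the monitoring itself would raise the deep-arm rate.

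That would push the comparison towards no difference, against the hypothesis. A null result could then mean either that deep block has no benefit or that the test stimulus hid part of one. The design has about 80% power and little to spare, so even a modest dilution would cost something. The planned two-group tests could not show it.

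**Working it through.** **The plan's own figure.** Inputs from the SAP: difference 0.032, SD 0.064, two-sided 5%, power 80%, equal groups.

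n per group = 2 × [0.064 × (1.960 + 0.842) / 0.032]² = 62.8, rounded up to 63. The stated size reproduces. Power by the two-sample t test is 79.5% at 63 per group, and 81.9% at 67 per group (134 split equally).

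**Is the imbalance in the text?** Yes, reading TOF=0 as a count of zero. The moderate target (count 1-2) does not trigger a PTC. The deep target (PTC 1-2) is read only by giving one. Both arms have the same induction rocuronium, so moderate-arm patients may also have a zero count at early checks or after a bolus. The imbalance is therefore mainly, not wholly, in the deep arm. The window length is not given. If it is 30-60 min (assumed), it holds 30/15 = 2 to 60/15 = 4 checks.

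**How large could a bias be?** The documents give no size or duration for an SPI response to PTC, so every input below except the two means is assumed. Let q be the share of PTCs that change titration, m the minutes affected in each 15, r the proportional rise in rate, and pD and pM the shares of checks with a PTC in the deep and moderate arms. The deep mean under the design difference is 0.192 − 0.032 = 0.160.

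Bias = q × (m/15) × r × (pD × 0.160 − pM × 0.192)

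- Low case (q 0.25, m 3, r 0.2, pD 0.8, pM 0.5): 0.25 × 0.2 × 0.2 × (0.128 − 0.096) = 0.00032, or 1.0% of 0.032. Power at 63 per group is 78.7%.
- High case (q 0.25, m 4.5, r 0.3, pD 1, pM 0.25): 0.25 × 0.3 × 0.3 × (0.160 − 0.048) = 0.00252, or 7.9% of 0.032. Power is 72.7%.
- High case with q = 1: 4 × 0.00252 = 0.01008, or 31.5%.
- A simpler version, with PTC in the deep arm only and the shift equal to 0.192 × r × m/15: r 10% for 1 min gives 0.00128 (4%); r 20% for 5 min gives 0.0128 (40%). No response gives 0.

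The answer is set by the assumptions.

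**Is the direction fixed?** No. In the first formula the bias is zero when pM = pD × 0.160/0.192. With pD = 0.8 that is 0.128/0.192 = 0.667, and above it the sign reverses.

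**Would a sensitivity analysis settle it?** The natural candidate drops a fixed interval after every scheduled check in both arms. If an effect lasts m minutes and k minutes are dropped, the fraction of the bias that remains is [(m − k)/(15 − k)] / (m/15).

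| Effect lasts | Dropped | Remaining |
|---|---|---|
| 4.5 min | 3 min | (1.5/12)/(4.5/15) = 42% |
| 4.5 min | 5 min | 0% |
| 6 min | 5 min | (1/10)/(6/15) = 25% |
| 10 min | 5 min | (5/10)/(10/15) = 75% |
| 15 min | 5 min | (10/10)/(15/15) = 100% |

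The 5-min version clears the bias only if the effect is assumed to be over within 5 min. The titration range is 30 SPI points wide, so a raised infusion target could stay in place while SPI remains in range. Agreement between the full and trimmed analyses would not clear PTC.

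Disagreement would not implicate it either. Checks can prompt rocuronium boluses, so trimming may also remove post-bolus time, and differently by arm. If a rise is followed by a compensating fall, trimming removes the rise and keeps the fall.

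**The case for a change.** The best case for acting is that the imbalance is built into the protocol, falls inside the primary window, and involves the kind of stimulus that the protocol says SPI responds to. Any bias through SPI would most plausibly run towards the null, where it could be mistaken for lack of benefit. Logging check times is cheap, and a secondary analysis leaves the primary one intact. Its cost is modest. With 5 min in 15 dropped, and all variation treated as independent minute-to-minute noise, the 95% CI half-width at 63 per group would rise from 0.0226 to 0.0276, and by much less if differences between patients dominate.

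The description of the imbalance stands, and so does the point about mechanism: section 1.1 gives less nociception as the reason for the expected saving, and the design does not separate that from the effect of the monitoring stimulus. The causal step remains unsupported. Section 1.2 speaks of surgical and painful stimuli in general, not of a brief wrist PTC under sevoflurane and remifentanil, and the oximeter site is not given. The low cost of the extra analysis does not rescue it, because neither possible result could be attributed to PTC.

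**Conclusion.** No change to the plan follows. At target depth PTC does fall mainly in the deep arm and within the primary window, but the existence, size and net direction of any bias are unknown from the documents, and zero is a credible value. The scenarios above, from nothing to 40% of 0.032, are illustrations on assumed inputs and bound nothing.

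PTC is the means by which a PTC target is confirmed, so it belongs to the deep-block strategy. The randomised comparison of the two strategies is unaffected. What is weaker is the step from a difference, or its absence, to a statement about surgical nociception. If the bias does run towards the null, a positive result would be conservative.

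The SAP also looks back on a trial already enrolled ("We enrolled a total of 134 patients to compensate for dropouts and observational variation"), so records not kept cannot now be created. If check times were recorded, a count of PTCs per arm in the primary window would be a sensible descriptive line beside the discussion of mechanism. It would alter no estimate and correct no figure or rule. The sample size of 63 per group is unaffected. This conclusion rests on reading TOF=0 as a count of zero, and on the absence from the documents of any evidence that PTC alters SPI-guided titration.

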Statistical analysis

Official title: Effects of deep neuromuscular block on surgical pleth index-guided remifentanyl administration in laparoscopic herniorrhaphy: A prospective randomized trial

NCT number: NCT04022733

Document date: Jan 18, 2022

Institution Name: Ajou University School of Medicine

The primary outcome was the infusion rate of remifentanil during pneumoperitoneum. Based on the findings of a previous study, we considered a difference in remifentanil infusion rate $>0.032 \mu\text{g}/\text{kg}/\text{min}$ (16% of mean infusion rate of remifentanil in moderate NMB under SPI-guided anesthesia for laparoscopic surgery [mean infusion rate of 0.192 (SD 0.064) $\mu\text{g}/\text{kg}/\text{min}$]) as clinically relevant. Based on a significance level of 5% and statistical power of 80%, each group required 63 subjects for analysis. We enrolled a total of 134 patients to compensate for dropouts and observational variation.

Statistical analyses were conducted using SPSS software version 25.0 (IBM, NY, USA). Data are presented as mean \pm SD, median (interquartile range), and number of patients. The normality of distribution was tested using the Kolmogorov–Smirnov/ the Shapiro–Wilk test. Continuous data were compared using a two-tailed t test when normally distributed; however, Mann-Whitney *U*-test was used for non-normally distributed data. Categorical data were compared using the Chi-square test or Fisher's exact test, as appropriate. Intergroup comparisons for repetitively measured data were performed by unpaired t-test with Bonferroni correction. *P*-values < 0.05 were considered statistically significant.

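### Does the mismatch between 0.032 µg/kg/min and 16% of 0.192 leave the trial short of its stated 80% power?

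*SAP*

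**What the plan says.** The sample-size paragraph of the SAP (Statistical analysis) is the only place in either document that gives a relevance threshold or a power figure. The absolute threshold is in the main clause: "we considered a difference in remifentanil infusion rate $>0.032" µg/kg/min. A parenthesis then describes it in relative terms as "16% of mean infusion rate of remifentanil in moderate NMB under SPI-guided anesthesia for laparoscopic surgery", and an inner bracket supplies the reference value, "mean infusion rate of 0.192 (SD 0.064" µg/kg/min). The resulting size follows: "Based on a significance level of 5% and statistical power of 80%, each group required 63 subjects for analysis". Enrolment was set at 134 in total to allow for losses, the same total as in section 1.3 (Study Design) of the protocol. For the analysis, the SAP says: "Continuous data were compared using a two-tailed t test when normally distributed". The Mann-Whitney test is the alternative, and significance is judged at P below 0.05.

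**The concern.** One sentence expresses the same threshold in two ways, and they differ. Ordinary rounding to the printed precision does not reconcile them: 16.67% rounds to 17%, and 0.0307 rounds to 0.031. Because this is the only benchmark for a worthwhile effect and the only basis for the 80% power, a reader could ask which value was meant. If it was 16%, the required size would be 69 or 70 per group, 63 would fall short of 80% power, and so would the full 134 with no dropouts. There would also be two yardsticks for judging the observed difference. Separately, the 63 comes from a normal approximation, whereas the SAP names a t test, for which the same inputs give 64.

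**Working it through.** **Inputs (all from the SAP, Statistical analysis).** Absolute difference 0.032; relative difference 16%; reference mean 0.192; SD 0.064; significance level 5%, taken as two-sided because the analysis test is two-tailed; power 80%; 63 per group needed; 134 enrolled. An equal split (67 per group) is assumed.

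**The two thresholds.**
- 0.032 / 0.192 = 0.1667, i.e. 16.7%.
- 0.16 × 0.192 = 0.03072.
- Gap: 0.032 − 0.03072 = 0.00128 µg/kg/min.

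**Reproducing the stated 63.** The normal-approximation formula is n per group = 2 × (1.960 + 0.842)² / d², with d = difference / SD.
- Absolute value: d = 0.032/0.064 = 0.50, so n = 2 × 7.849 / 0.25 = 62.8, rounded up to **63**. This is the SAP's figure.
- Relative value: d = 0.03072/0.064 = 0.48, so n = 2 × 7.849 / 0.2304 = 68.1, rounded up to 69. This is not the SAP's figure.
- A one-sided test at 0.032 would give 50, which also does not match.

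The t test (noncentral t) gives 63.8 (64) at d = 0.50 and 69.1 (70) at d = 0.48.

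**Power.** Normal formula: Φ(d × √(n/2) − 1.960). For example, d = 0.50 with n = 63 gives Φ(2.806 − 1.960) = Φ(0.846) = 80.1%.

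| Difference | n per group | Normal | t test |
|---|---|---|---|
| 0.032 | 63 | 80.1% | 79.5% |
| 0.032 | 67 | 82.5% | 81.9% |
| 0.03072 | 63 | 76.9% | 76.2% |
| 0.03072 | 67 | 79.3% | 78.8% |

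**Could 0.032 itself be a rounded value?** A difference between 0.0315 and 0.0317 would print as 0.032 and also as 16% (0.165 × 0.192 = 0.03168). At those two ends the normal formula needs 65 per group, so this reading does not give 63 either. It would leave normal-formula power at 63 per group at 78.9% to 79.3%.

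**Does the gap matter for interpretation?** With 63 per group and SD 0.064, the standard error of the difference is 0.064 × √(2/63) = 0.0114, and the 95% confidence interval has a half-width of about 1.96 × 0.0114 = 0.0223. The gap of 0.00128 is about 6% of that half-width (0.00128/0.0223), too small for the trial to resolve.

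**Dropout allowance.** 134 − 2 × 63 = 8 patients, or 8/134 = 6.0%. Three losses in each arm still leave 64 per group, the t-test requirement at 0.032.

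**The case for a change.** The case for acting is that the error is real, can be checked from the page, and sits in the primary design assumption. A reduction between 16.0% and 16.7% of 0.192 would pass one version of the threshold and fail the other. Under the 16% version, neither formula reaches 80% power at 63 or at 67 per group, and the correction costs one sentence.

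The arithmetic of this stands in full. The inference to a power shortfall does not. It needs 16% to be the planning value, and the stated 63 rules that out: only the absolute figure reproduces it. The absolute figure is also in the main clause and is a round fraction of both reference quantities (half of 0.064, one sixth of 0.192). Part of the apparent drop from 80% to 76% comes from switching formula: on the normal formula behind the 63, it is 76.9%.

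The 63-versus-64 point is a choice between two standard planning formulas worth about half a percentage point, and enrolling 134 covers it. The two-yardsticks point is fair in principle, but the SAP attaches no decision to the threshold, and the two values are far closer together than the trial's own precision.

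**Conclusion.** The parenthetical percentage is off by under one percentage point (16% printed, 16.7% correct), and that is the whole of the error. The difference used was 0.032 µg/kg/min. It reproduces 63 per group, and the power claim holds at that value: 80.1% (normal) or 79.5% (t test) at 63, rising to 82.5% or 81.9% if all 134 are analysed in equal arms. The figures of 76% and 79% belong to a threshold that the plan's own sample size shows was not used, so they should not be reported as a shortfall.

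This is a clerical slip, probably 16.67% truncated, though the documents do not say how the percentage was obtained. Correcting it would change no sample size, power statement, test or conclusion. The SAP is dated January 2022 and describes enrolment in the past tense, so the size is settled in any case. The conclusion rests on a two-sided 5% test, SD 0.064 in both groups, and equal allocation. No change to the plan follows.

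### Bonferroni correction of the repeatedly measured data is valid, but Holm's method on the same family of comparisons keeps the 5% guarantee and never rejects less

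*SAP*

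**What the plan says.** The SAP (Statistical analysis) gives one sentence on repeated measurements: "Intergroup comparisons for repetitively measured data were performed by unpaired t-test with Bonferroni correction". The general threshold is P-"values < 0.05 were considered statistically significant", and sidedness comes from the sentence on continuous data: "Continuous data were compared using a two-tailed t test when normally distributed".

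The SAP does not say which variables are measured repeatedly, how many time points there are, or whether the correction runs within each variable or across several. Neither document uses the word secondary for these data.

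The only outcome named is the primary one. The SAP has "The primary outcome was the infusion rate of remifentanil during pneumoperitoneum", and Protocol section 1.3 gives the same rate over the interval from pneumoperitoneum to removal of the laparoscope. That is one summary value per patient. The sample size is tied to it: "Based on a significance level of 5% and statistical power of 80%, each group required 63 subjects for analysis".

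**The concern.** Bonferroni holds every comparison to 0.05 divided by the number of comparisons, even after other comparisons in the family have been declared different. Once some null hypotheses are rejected, fewer remain that could yield a false positive, and part of the 5% allowance goes unused. Holm's method spends that allowance without needing any further assumption.

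What is at stake is limited: which individual time points are declared different when a real difference is present at several of them. That pattern is plausible here, because Protocol section 1.3 keeps the block at its target depth through surgery and has remifentanil adjusted continuously.

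**Working it through.** **1. The plan's own figure.** Inputs from the SAP: difference 0.032, SD 0.064, two-sided 5%, power 80%.

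n per group = 2 × (1.960 + 0.842)² × (0.064/0.032)² = 2 × 7.85 × 4 = 62.8, rounded up to 63.

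The stated 63 is reproduced. It uses one comparison at an unadjusted 5%, so the repeated-measures correction does not enter it.

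**2. The two rules.** For K comparisons:
- Bonferroni rejects comparison j if p(j) ≤ 0.05/K.
- Holm sorts the p values upward and rejects the i-th smallest as long as it, and every smaller one, meets p ≤ 0.05/(K − i + 1).

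For K = 5, Bonferroni uses 0.01 throughout. Holm uses 0.01, 0.0125, 0.0167, 0.025 and 0.05 in turn. Two results follow:
- Any p value at or below 0.05/K also meets its Holm threshold, so Holm rejects everything Bonferroni rejects.
- If no p value reaches 0.05/K, Holm stops at its first step. The chance of at least one rejection is therefore identical.

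**3. Why Holm keeps 5%.** Suppose m of the K null hypotheses are true. When Holm first rejects a true one, at most K − m others have been rejected, so the threshold at that step is at most 0.05/m. A family-wise error therefore needs some true-null p value at or below 0.05/m. The chance of that is at most m × 0.05/m = 0.05. The step only adds probabilities, so it holds under any correlation.

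**4. Size of the gain (illustrative).** The 63 per group and the 0.5 SD effect (0.032/0.064) are borrowed from the primary outcome. K, the correlation and complete data are assumed.

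The noncentral t distribution gives power at one time point of 57.6% at 0.01 and 79.5% at 0.05. With K = 5, Holm must lie between these. Simulation with pooled two-sided t tests and equal correlation between time points used 20,000 trials per setting (10,000 for K = 8):

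| K | Truly different | Bonferroni, power per such time point | Holm | Gain (points) |
|---|---|---|---|---|
| 5 | 1 | 57–58% | 57–58% | about 0.1 or less |
| 5 | 2 | 57–58% | 59–60% | about 2 |
| 5 | 3 | 57–58% | 61–62% | about 4 |
| 5 | 4 | 57–58% | 64% | 6 to 7 |
| 5 | 5 | 57–58% | 67–68% | about 10 |
| 3 | 3 | 65–66% | 73–74% | about 8 |
| 8 | 4 | 51% | 54% | about 3 |
| 8 | 8 | 51–52% | 61–63% | 10 to 12 |
| 10 | 10 | 48–49% | 59–60% | 11 to 12 |

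Correlation was 0.3, 0.5 and 0.7 (0, 0.5 and 0.8 for K = 8). At correlation 0.8 with K = 3 the gain falls to 71.7 − 64.9 = 6.8 points.

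Further results for K = 5, at correlation 0.3/0.5/0.7:
- Declaring all five when all five differ: 16/23/31% with Bonferroni, 39/47/54% with Holm.
- At least one significant time point when all five differ: 94/89/82% with either method.
- Family-wise error, none different: 4.6/4.2/3.6% with either.
- Family-wise error, two different: 3.0/2.9/2.3% with Bonferroni, 3.9/3.9/3.1% with Holm.
- Family-wise error, four different: 0.9/1.0/1.0% with Bonferroni, 2.8/3.0/2.9% with Holm.
- Other effect sizes, all five different at 0.3/0.4/0.6 SD: 18/36/77% with Bonferroni, 21–23/43–44/85–87% with Holm.

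Across all settings, Holm's family-wise error never exceeded 5.0%, and no trial had a Bonferroni rejection that Holm missed.

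**5. What happens if the family is narrowed.** Suppose Bonferroni now spans three variables and Holm is applied to each variable separately. With three independent variables, no true effects and 4.2% error in each (the value above at correlation 0.5), the chance of any false positive is 1 − (1 − 0.042)³ = 1 − 0.879 = 12%.

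**The case against.** The strongest reply is that nothing here is broken: Bonferroni is valid and conservative, and preferring another valid method is a matter of taste. The first half stands. Taste does not explain the second half, because on the same family Holm is never worse in rejections and gives the same guarantee.

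Four further objections stand in whole or in part:
- **Family.** The advantage is guaranteed only if the family is unchanged, and the SAP does not define it. Switching to Holm while also restricting the correction to each variable could weaken protection, as step 5 shows.
- **Size.** The larger gains need a 0.5 SD difference at every time point. Nothing in the documents supports that effect for unnamed variables.
- **Intervals and simplicity.** Bonferroni gives simple matching simultaneous confidence intervals and judges each time point on its own p value. The SAP's list of data summaries mentions no such intervals, but silence does not rule them out. Someone who wants them has a fair reason to keep Bonferroni.
- **Timing.** The SAP is dated January 2022 and written in the past tense. If the tests have been run, rewording the sentence would misdescribe what was done.

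A reader might infer more than the documents support. One such inference is that within-patient correlation invalidates the Bonferroni-corrected t tests. It does not: each test compares different patients at one time point, and Bonferroni holds under any dependence. Another is that the primary result or the sample size is weakened. Both rest on a single summary per patient outside this correction.

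**Conclusion.** This is a cheap improvement, not an error. The direction is certain: on the same p values and the same family, Holm keeps family-wise error at 5% and rejects at least as much as Bonferroni. That needs only valid individual p values, which Bonferroni needs too.

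The size is uncertain and runs from nothing to about 12 points of power per time point, depending mainly on how many time points truly differ. It cannot be fixed from the documents, which give no number of time points, correlation or effect for these data. It would be wrong to conclude that Holm makes it likelier to find any difference on a variable, because its first step is Bonferroni's.

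That these data are secondary is a reasonable inference from the single named primary outcome, not a statement in the plan. The primary analysis and the 63 per group stand as they are.

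**What to change.** In the SAP sentence on repeatedly measured data, replace the words Bonferroni correction by Holm correction (two-sided, family-wise 5%). Apply it to exactly the comparisons the Bonferroni correction covers, and add a sentence stating that family: the variables, their time points, and whether the correction runs within or across variables. If Bonferroni covers the time points within each variable, Holm should too. If it spans variables, Holm must span the same ones. Do not narrow the family when switching. The unpaired t tests and the primary analysis stay as they are.

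The cost is one phrase and one clarifying sentence, with no new patients, data or model; Holm needs only the sorted p values. The family has to be stated under either method. What is given up is simple matching simultaneous confidence intervals; if these are wanted, keep Bonferroni and say so. If the analysis is already done, leave the Bonferroni results as the planned ones and report any Holm results beside them, labelled post hoc.
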